1.2.4 Clinical Efficacy

1.2.4.1 NAV3-23 (SC)

This was an open-label, multicenter study of Tc 99m tilmanocept by subcutaneous injection in patients with active RA and healthy controls. Tilmanocept was administered SC at 1 of 2 mass doses: [1] 50 mcg (Cohorts 1 & 3), or [2] 200 mcg (Cohorts 2 & 4). Both mass doses were radiolabeled with 2 mCi of Tc 99m. A total of 18 subjects were enrolled and evaluated (9 active RA, 9 HC). Imaging was performed 60 ± 15 minutes post injection. The following performance conclusions were drawn upon study completion:

- Based on data from this study and parallel pathology studies, Tc 99m tilmanocept localizes to activated macrophage-infiltrated joints at doses of 50 mcg and 200 mcg radiolabeled with 2.0 mCi (74.0 MBq) by SC administration.
- Across all combined RA subjects, swollen/tender joints demonstrating the highest proportions of localization include the wrists and knees.
- Based on qualitative image evaluation, Tc 99m tilmanocept does not show differences in localization between 2 to 3 and 4 to 6-hour planar imaging within dosing groups.

^b Maximum observed excretion rate, calculated as (radioactivity*volume)/ (end time – start time).

- Tc 99m tilmanocept demonstrates a greater frequency of localization to swollen/tender joints at 200 mcg/2.0 mCi than 50 mcg/2.0 mCi.
- There is an overall lack of concordance between qualitative observation of Tc 99m tilmanocept localization to swollen/tender joints identified in DAS28 joint count assessment. Swollen/tender joints did not appear to be reliable predictors of presumed abnormal activated macrophage infiltration and overall disease progression when used as an isolated diagnostic system.
- Increased tilmanocept mass dosing, increased Tc 99m specific activity, and other routes of administration may enhance localization and anatomic delineation in tilmanocept-positive joints of RA patients.
- The potential for using Tc 99m tilmanocept to delineate macrophage infiltration in RA-affected joints may allow for earlier RA-specific treatment beyond the current standard of care ACR/EULAR criteria.

1.2.4.2 NAV3-21 (IV)

This was an open-label, multicenter, dose-escalation safety with PK and dosimetry study of Tc 99m tilmanocept by IV injection in HCs and subjects with active RA. Thirty-nine subjects were enrolled. A total of 27 subjects with active RA were enrolled to Groups 1 to 9 in the dose escalation phase. Group 10 consisted of 6 HCs (3 female and 3 male) and Group 11 consisted of 6 subjects with active RA (3 female and 3 male). Tilmanocept was administered IV at 1 of 3 mass doses: 50 mcg, 200 mcg, or 400 mcg. Within each mass dose group, tilmanocept was radiolabeled with 1 of 3 Tc 99m doses: 1 mCi, 5 mCi, or 10 mCi. Subjects in Groups 10 and 11 received the maximum dose of 400 mcg/10 mCi. Imaging was performed 60 ± 15 minutes after injection. The following clinical efficacy conclusions were drawn upon study completion:

- The TUV_{brain(average)} readout provides an objective means of quantification of Tc 99m tilmanocept localization when administered at the calculated optimal dose of 150 mcg/10 mCi and planar images are acquired 60 to 180 minutes after drug administration.
- Joint-specific localization of activity and joint-specific clinical symptomology were not fully concordant. Within the spectrum of RA disease involvement, there may be a decoupling of the causal active immune process and subsequent clinical sequelae. We surmise that imaging and quantification of Tc 99m tilmanocept uptake may provide a fuller and more accurate, responsive, and objective measure of RA disease activity than can be obtained from clinical assessments alone. Future studies will examine whether the approach to image acquisition and calculation of TUV can be further refined.

1.2.4.3 NAV3-31 (IV)

This was an open-label, multi-center, single and repeat-dose study designed to evaluate the reliability and sensitivity of TUV assessments in HCs and subjects with active RA. One hundred and sixteen evaluable subjects were enrolled. Tilmanocept was administered IV

at a dose of 150 mcg tilmanocept radiolabeled with 10 mCi Tc 99m. Clinical efficacy conclusions for this study are still in progress.

1.2.5 Clinical Safety

1.2.5.1 NAV3-23 (SC)

The NAV3-23 (NCT02683421) safety evaluation included all trial subjects injected with Tc 99m tilmanocept (N = 18). The AE monitoring was performed from the time of dose administration until completion of onsite safety assessment. There was 1 AE that was possibly related to and 1 AE that was probably related to Tc 99m tilmanocept. However, there were no AEs that led to trial discontinuation, and no SAEs were observed. There were no deaths on trial.

1.2.5.2 NAV3-21 (IV)

The primary safety endpoint of the NAV3-21 study was evaluated by examining the incidence of AEs, changes over time in clinical laboratory tests, physical exams, electrocardiogram (ECG) parameters, and vital signs. The safety evaluation included all subjects who were enrolled in the study and administered Tc 99m tilmanocept (n = 39). There were no Tc 99m tilmanocept related AEs. There were no deaths during the trial; no SAEs; and no AEs that led to discontinuation from the trial. In addition, radiation exposure was within regulatory and safety limits at the doses evaluated. Radiation exposure and pharmacokinetics do not appear to differ in subjects with RA and healthy control subjects.

1.2.5.3 NAV3-31 (IV)

The primary safety endpoint of the NAV3-31 study was evaluated by examining the incidence of AEs, changes over time in clinical laboratory tests, electrocardiogram (ECG) parameters, and vital signs. The safety evaluation included all subjects who were enrolled in the study and administered Tc 99m tilmanocept (n = 116). There were no Tc 99m tilmanocept related AEs. There were no deaths during the trial; there were three SAEs that were not related to study drug or study procedures; and one AE that led to discontinuation from the trial. There were no Adverse Drug Reactions reported.

2 STUDY OBJECTIVES

2.1 Primary Objectives

- To demonstrate that global tilmanocept uptake values (TUV_{global}) obtained before initiation of anti-TNFα therapy (TUV_{global[b]}) and at 5 weeks ± 1 week following change in therapy (TUV_{global[5w]}) has a specificity of greater than 80% to correctly specify a clinical non-response to therapy at 24 weeks.
- To demonstrate that TUV_{global} obtained before initiation of anti-TNF α therapy and at 5 weeks \pm 1 week following change in therapy has a sensitivity of greater than 65% to correctly classify a positive clinical response to therapy at 24 weeks.

2.2 Key Secondary Objective

• To evaluate the negative predictive value (NPV) of TUV_{global} obtained before initiation of anti-TNFα therapy (TUV_{global[b]}) relative to a clinical non-response to therapy at 24 weeks.

2.3 Secondary Objectives

- To evaluate the sensitivity and specificity of TUV_{global} obtained before initiation of anti-TNFa therapy and at 5 weeks ± 1 week following change in therapy relative to a positive clinical response or a non-response to therapy at 12 weeks.
- To evaluate the NPV of TUV_{global[b]} relative to a clinical a non-response to therapy at 12 weeks.
- To evaluate the positive predictive value (PPV), negative predictive value (NPV), and overall accuracy (OA) of TUV_{global} obtained before initiation of anti-TNF α therapy and at 5 weeks \pm 1 week (ΔTUV_{global}) following change in therapy relative to a positive clinical response or a non-response to therapy at 12 and/or 24 weeks.
- To evaluate the qualitative assessment of Tc 99m tilmanocept imaging to predict clinical response or non-response following a change in anti-TNFα therapy.
- To evaluate the additive effect of either quantitative or qualitative assessment of Tc 99m tilmanocept imaging to the other at baseline and change from baseline to 5 weeks \pm 1 week to predict clinical response or non-response following a change in anti-TNF α therapy.
- To evaluate the correlation of changes in TUV_{global} obtained before initiation of anti-TNF α therapy and at 5 weeks \pm 1 week following a change in therapy with changes in composite clinical assessments and their constituent parameters at 12 and/or 24 weeks.
- To evaluate the correlation of changes in TUV_{global} obtained before initiation of anti-TNF α therapy and at 5 weeks \pm 1 week following a change in therapy with changes in clinical assessments at 12 and/or 24 weeks for specific anti-TNF α bDMARD agents.
- To evaluate the correlation of changes in TUV_{global} and changes in clinical RA assessments as a means to monitor therapy.

- To evaluate sensitivity and specificity in patient subgroups.
- To evaluate safety of IV-administered tilmanocept radiolabeled with Tc 99m.

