3 INVESTIGATIONAL PLAN

3.1 Overall Study Design and Plan

This is a prospective, open-label, multicenter study designed to evaluate the predictive capacity of Tc 99m tilmanocept planar imaging for downstream clinical response(s) in individuals with moderate to severe RA who are candidates for change in anti-TNF α therapy. Temporal (Baseline to 5-week) changes in quantitative imaging will be correlated with longitudinal (Baseline to 12- and 24-week) assessments of clinical RA outcomes to evaluate the clinical utility of Tc 99m tilmanocept for the expedited evaluation of antirheumatic treatment efficacy when compared with longitudinal assessments in clinical practice.

Prior to the initiation of a new therapy, subjects will undergo baseline rheumatological evaluations of ACR/EULAR 2010 Classification Criteria, CDAI, DAS28, HAQ-DI[©], and a serological RA panel for the characterization of disease activity. Following these evaluations, subjects will receive an IV dose of 150 mcg tilmanocept radiolabeled with 10 mCi of Tc 99m and undergo baseline planar imaging of the bilateral hands and wrists beginning 60-75 minutes following Tc 99m tilmanocept administration. Upon completion of baseline imaging procedures, subjects will commence a new anti-TNF α bDMARD treatment regimen and return to the clinic 5 \pm 1 weeks later for a series of rheumatological evaluations (including CDAI, DAS28, ACR Response Criteria, and HAQ-DI[©]), drug administration, and bilateral hand/wrist imaging. The rheumatological evaluations will be repeated at 12 \pm 1 weeks and 24 \pm 1 weeks after commencement of the new therapy.

Images will undergo centralized quantification for the derivation of joint-specific and global tilmanocept uptake values (TUV). At the joint level, TUV is defined as the intrasubject ratio of the average pixel intensity of a joint to the average pixel intensity of the reference region. TUV_{global} is a per subject summary of TUV_{joint} values greater than the upper 95th percent (2 standard deviations) of the normative database representing RA-specific inflammation. TUV calculations are additionally described in the Statistical Analysis Plan.

All images will be read by three nuclear medicine specialists trained in the reading of these images. Each reader will work independently of the other readers and will be blinded to clinical assessments. Each reader will provide both a qualitative read and map regions of interest for calculation of TUVs.

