- To evaluate the additive effect of either quantitative or qualitative assessment of Tc 99m tilmanocept imaging to the other at baseline and change from baseline to 5 weeks \pm 1 week to predict clinical response or non-response following a change in anti-TNF α therapy.
- To evaluate the correlation of changes in TUV_{global} obtained before initiation of anti-TNFα therapy and at 5 weeks ± 1 week following a change in therapy with changes in composite clinical assessments and their constituent parameters at 12 and/or 24 weeks.
- To evaluate the correlation of changes in TUV_{global} obtained before initiation of anti-TNF α therapy and at 5 weeks ± 1 week following a change in therapy with changes in clinical assessments at 12 and/or 24 weeks for specific anti-TNF α bDMARD agents.
- To evaluate the ability of changes in TUV_{global} obtained before initiation of anti-TNF α therapy and at 12 weeks ± 1 week following change in therapy to accurately predict a clinical response or non-response at 24 weeks.
- To evaluate the correlation of changes with TUV_{global} and changes in clinical RA assessments as a means to monitor therapy.
- To evaluate sensitivity and specificity in patient subgroups.

• To evaluate the safety of IV-administered tilmanocept radiolabeled with Tc 99m.

The statistical endpoints that address these objectives are defined in Section 4 (efficacy) and Section 5 (safety). Refer to Section 2.2.1 for subgroup definitions and considerations.

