4.2.3 Analysis of Secondary Efficacy Variables

All RA quantitative assessment variables (CDAI, ACR Response Criteria component scores, DAS28 score, and HAQ-DI) will be summarized by computing the mean, standard deviation, number of observations, minimum, median, and maximum for the observed values at each time point and for the change from baseline for values collected after Day 0. The ACR Response Criteria will be summarized with a frequency table of the highest ACR Response level (None, ACR20, ACR50, ACR70) attained by that patient at that time point. That is, a patient who satisfies ACR50 also satisfies ACR20 but will not appear in the frequency count for ACR20.

The qualitative assessments will be summarized in a 2 by 2 contingency table displaying the cell frequencies and marginal totals by reader as shown in section

4.2.1 above. The PPV and NPV of the predicted response will be calculated for each reader, as will the OA. In addition, 95% exact confidence intervals will be provided for each of these parameters. Observed significance levels (p-values) for the exact binomial (Clopper-Pearson) tests of PPV and NPV (see sections 1.3 and 4.2.1 above) will be provided for each reader. These tests will be based on PPV of the predicted response greater than 0.65, and NPV of the predicted response greater than 0.7.

Concordance of improvement classification for: 1) $\Delta TUV_{global[5w]}$ bucketing and 2) $\Delta TUV_{global[12w]}$ bucketing with clinical criteria (ACR Response, CDAI, DAS28, and HAQ-DI) will be analyzed as follows. Note that the concordance of $\Delta TUV_{global[5w]}$ bucketing with ACR50 at 24 weeks is evaluated as co-primaries (sensitivity and specificity). For each of the RA improvement criteria, a cross-classification table will be provided. The PPV, NPV, sensitivity, specificity, and OA will be calculated and 95% exact (Clopper-Pearson) confidence intervals will be provided. Observed significance levels (p-values) for the exact binomial (Clopper-Pearson) tests for sensitivity and specificity will be provided for each reader.

Figures displaying the ΔTUV_{global} by time point (5, 12, and 24 weeks) will be created to display the relationship between ΔTUV_{global} over time with the corresponding clinical response assessment (ACR20/50/70, DAS28, and CDAI) at the given time point.

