The Kendall rank correlation between $\Delta TUV_{global[5w]}$ with $\Delta CDAI_{12w}$ and $\Delta CDAI_{24w}$ will be computed and a 95% confidence interval for its value will be computed using Fisher's Z-transformation. Similarly, the Kendall rank correlation between $\Delta TUV_{global[5w]}$ with changes from baseline in DAS28 and in each of the ACR Response Criteria components at weeks 12 and 24 will be computed and a 95% confidence interval for its value will be computed using Fisher's Z-transformation. The marginal distributions of the variables will be characterized with the mean, standard deviation, and the number of data pairs.

The additive effect of either quantitative or qualitative assessment of Tc 99m tilmanocept imaging will be assessed with a generalized linear mixed model with the logit link function. The patient's response status will be used as the response variable. Fixed model terms for the quantitative and qualitative plus quantitative assessments will be used. The quantitative assessment will be based on $\Delta TUV_{global[5w]}$ bucketing. Random terms will be fit for the subject and reader within subject using the variance component model. A table displaying the partial hypothesis tests (Type 3 test) for the fixed effects will be displayed.

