STATKING Clinical Services (DD-MMM-YYYY)

Source Program: xxxxxx.sas

Table format is repeated for each reader. Entire table (all parts) is repeated for the PP population (table 34).

Table 35. Summary of Generalized Linear Mixed Model to Asses the Additive Effect of either Quantitative or Qualitative Assessment of Tc 99m Tilmanocept Imaging on Patient Response Status at Week 12 Navidea Biopharmaceuticals - Study No. NAV3-33

ITD Population (N=xxx)

Model Termª	Parameter Estimate ^b	Standard Error	95% Confidence Limits	p-value ^c
Quantitative Imaging Assessment	xxx.xxx	****	(xxx.xxx, xxx.xxx)	x.xxxx
Qualitative plus Quantitative Imaging Assessment	xxx.xxx	****	(xxx.xxx, xxx.xxx)	x.xxxx

^a Indicator variable for prediction of "Improved" compared to the reference category of "Not Improved."

^b Estimate calculated from a generalized linear mixed model with the logit link function with patient response status as the response variable, fixed terms for quantitative and qualitative plus quantitative imaging assessment, and random terms for subject and reader within subject using a variance component model.

 $^{\circ}$ Based on a two-sided t-test.

STATKING Clinical Services (DD-MMM-YYYY) Source Program: xxxxxx.sas

Table is repeated for the PP population (table 36) and for tables 37 – 38.

Page x of y

Table 39. Number and Percentage of Patients with TEAEs Navidea Biopharmaceuticals - Study No. NAV3-33 Safety Population (N=xxx)

Adverse Event Category ^a :	Overall (N=xxx)			
Total Number of TEAEs	XXX			
Patients with at Least One TEAE	xxx (xxx%)			
System Organ Class 1 Preferred Term 1	xxx (xxx%) xxx (xxx%)			
Preferred Term 2	xxx (xxx%)			
System Organ Class 2	xxx (xxx%)			
Preferred Term 1	xxx (xxx%)			
Preferred Term 2	xxx (xxx%)			

Table 40. Summary of TEAEs Navidea Biopharmaceuticals - Study No. NAV3-33 Safety Population (N=xxx)

	Overall
	(N=xxx)
Patients With at Least One TEAE	XXX
Maximum TEAE Severity Grade	
Mild	xxx (xxx%)
Moderate	xxx (xxx%)
Severe	xxx (xxx%)
Highest Relationship of TEAE to Tc 99m tilmanocept	
Definitely Not [n(%)]	xxx (xxx%)
Probably Not [n(%)]	xxx (xxx%)
Possibly [n(%)]	xxx (xxx%)
Probably [n(%)]	xxx (xxx%)
Definitely [n(%)]	xxx (xxx%)
Highest Relationship of TEAE to Study Procedure	
Definitely Not [n(%)]	xxx (xxx%)
Probably Not [n(%)]	xxx (xxx%)
Possibly [n(%)]	xxx (xxx%)
Probably [n(%)]	xxx (xxx%)
Definitely [n(%)]	xxx (xxx%)
Patients with at Least One TESAE	xxx (xxx%)

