XXXX	XXXXXX	XXXXX	XXXXXX	XXXXXX	****	XXXXXXX	XXXXXX	XXXX	****

STATKING Clinical Services (DD-MMM-YYYY) Source Program: xxxxxx.sas

Page x of y

Data Listing 24. Study Drug Administration Data Listing Navidea Biopharmaceuticals - Study No. NAV3-33 Safety Population (N=xxx)

Patient No.	Date/ Time of Injection	Anatomic Location of Injection	Pre-Injection Radioactivity (mCi)/Time of Measurement	Post- Injection Radioactivity (mCi)/Time of Measurement	Calculated Amount of Administered Radioactivity (mCi)	Calculated Mass Dose (µg)	Volume Injected (mL)	Lot Number
XXXX	xxxxxxxx/ xxxx	XXXXXXXX	xxx/ xxxx	xxx/ xxxx	XXX	XXX	XXX	XXX
XXXX	xxxxxxxxx/ xxxx	*****	xxx/ xxxx	xxx/ xxxx	xxx	XXX	XXX	XXX
	xxxxxxxxx/ xxxxx	*****	xxx/ xxxx	xxx/ xxxx	XXX	XXX	XXX	XXX

Data Listing 25. Post-Injection Imaging Data Listing Navidea Biopharmaceuticals - Study No. NAV3-33 Safety Population (N=xxx)

Patient No.	Visit	Date of Imaging	Start Time of Imaging	SPECT/CT Image Finding
XXXX	*****	XXXXXX	xx:xx	XXX
XXXX	*****	XXXXXX	xx:xx	XXX

Data Listing 26. SPECT/CT Reader Results Data Listing - Hands and Wrists Navidea Biopharmaceuticals - Study No. NAV3-33 Safety Population (N=xxx)

Patient	Post-Injection		SPECT/CT
No.	Imaging Time Point	Joint	Image Finding
XXXX	XXXXXXX	XXXXXXXXXXXX	XXXX
		XXXXXXXXXXXX	
XXXX	XXXXXXX	XXXXXXXXXXXX	XXXX
		XXXXXXXXXXXX	

Data Listing 27. TUV Data Listing Navidea Biopharmaceuticals - Study No. NAV3-33 Safety Population (N=xxx)

		TUV Classification of Improvement					
Patient No.	Reader No.	Algorithms Predicting Improvement ^a	Algorithms Predicting No Improvement ^a	Visit	Date/Time	Region of Interest ^b	TUV
XXXX	X	X, X	X	XXXXXXX	XXXXXX	XXXXXX	XXXXX
				XXXXXXX	XXXXXX	XXXXXX	XXXXX
				XXXXXXX	XXXXXX	XXXXXX	XXXXX
				XXXXXXX	XXXXXX	XXXXXX	XXXXX
				XXXXXXX	XXXXXX	XXXXXX	XXXXX
XXXX	X	X	x, x	XXXXXXX	XXXXXX	XXXXXX	XXXXX

^a 1 = Change in Global TUV[5w] Bucketing, 2 = Change in Global TUV[12w] Bucketing
^b Region of Interest is joint or Global.
STATKING Clinical Services (DD-MMM-YYYY)

Source Program: xxxxxxx.sas

Data Listing 28. Qualitative Assessment Data Listing Navidea Biopharmaceuticals - Study No. NAV3-33 Safety Population (N=xxx)

Patient No.	Reader No.	Qualitative Assessment ^a	Date/Time
XXXX	x	XXXXXXX	xxxxxxxx/
XXXX	Х	XXXXXXX	xxxxxxxx/ xxxx

^a Qualitative Assessment is either "Improved" or "Not Improved." STATKING Clinical Services (DD-MMM-YYYY) Source Program: xxxxxx.sas

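### The objective on what the visual and quantitative reads add to each other includes baseline, but no SAP output addresses the baseline part

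*Protocol*

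**What the plan says.** Protocol 2.3 lists as a secondary objective the "additive effect of either quantitative or qualitative assessment of Tc 99m tilmanocept imaging to the other at baseline and change from baseline" to Week 5, as a predictor of clinical response or non-response. SAP 1.0 keeps the baseline element: "imaging to the other at baseline and change from baseline to 5 weeks".

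Protocol 3.1 has three independent readers read all images, which includes the baseline images: "Each reader will provide both a qualitative read and map regions of interest for calculation of TUVs".

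The SAP uses those reads as follows.

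- **Additive model (4.2.3, Tables 35-38).** A logit mixed model. "Fixed model terms for the quantitative and qualitative plus quantitative assessments will be used". "The quantitative assessment will be based on $\Delta TUV_{global[5w]}$ bucketing". The Table 35 shell codes each term as "Indicator variable for prediction of 'Improved' compared to the reference category of 'Not Improved".
- **Visual read alone (4.2.3, Tables 21-24).** "The qualitative assessments will be summarized in a 2 by 2 contingency table displaying the cell frequencies and marginal totals by reader". The text does not say which scan or scans the assessment rests on.
- **Listing 28.** Columns for patient, reader, assessment and date/time, with no visit column. Its footnote reads "Qualitative Assessment is either 'Improved' or 'Not Improved".
- **Baseline TUV alone (4.1.1.1, Tables 11-14).** A cut-off of 5 on TUVglobal[b], reported for NPV only, with no visual read beside it.

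**The concern.** The objective names two occasions, baseline and the change to Week 5. The quantitative side has a stand-alone baseline rule that carries the key secondary endpoint. The visual side has no defined baseline prediction, and the only model that joins the two sides works from the Week 5 result.

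The baseline scan is the only imaging result available before the new anti-TNFα agent starts. Whether a visual read improves on the cut-off of 5 at that point, or the cut-off improves on the visual read, is what the baseline half of the objective asks. Without a defined variable and analysis, any answer would have to be built after the data are known.

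**Working it through.** No figure in the plan is at issue, so the check traces the objective through the SAP. One illustrative precision calculation follows.

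**1. What the baseline question needs.** For each reader: a baseline visual prediction V, the baseline rule Q = (TUVglobal[b] < 5), and Week 24 ACR50. The additive effect is how the outcome depends on V given Q, and on Q given V.

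**2. What the SAP provides (4.1.1.1, 4.2.3, 7.0 and Appendix B).**

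| Output | Visual input | Quantitative input | Baseline visual read identified? |
|---|---|---|---|
| Tables 11-14 | none | TUVglobal[b] alone; Week 5 bucket | no |
| Tables 21-24 | Improved / Not Improved | none | no |
| Tables 25-28 | within the combined call | within the combined call | no |
| Tables 35-38 | within the combined call | Week 5 bucket, combined call | no |
| Listing 28 | Improved / Not Improved, no visit | none | no |
| Listing 29 | within the combined call | original quantitative result | no |

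Outputs using the qualitative read: 4 + 4 + 4 = 12 tables, plus 2 listings, giving 14. Those identified as a baseline visual read: 0. Those pairing one with TUVglobal[b]: 0. Week 12 and Week 24 in the titles of these tables date the clinical outcome, not the scan.

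**3. Can the baseline part be recovered from the bucket?** Under algorithm 1 (SAP 4.1.1.1):

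- TUVglobal[b] < 5 gives N
- TUVglobal[b] ≥ 5 and change ≤ -10% gives Y
- TUVglobal[b] ≥ 5 and change > -10% gives N

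The model sees only Y against N. A patient below 5 and a patient at or above 5 with no fall carry the same value, so the coefficient cannot be split into a baseline part and a change part.

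**4. Can it be recovered from the visual call?** If the call is made with both scans in view, what the reader would have said from the baseline scan alone cannot be reconstructed. If it is meant to rest on the baseline scan, the SAP does not say so, and no output sets it against TUVglobal[b] < 5.

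**5. What a baseline comparison could deliver (illustration).** The planned 600 completers at 5:1 give a non-response proportion of 500/600 = 0.833. The documents give no rate of disagreement between V and Q; assume 10-20%. That is 60-120 discordant patients per reader. Split evenly by direction, it is 30-60 in each. If disagreement carries no information, the 95% Clopper-Pearson intervals are:

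- n = 30, 25 non-responders: 0.653 to 0.944, half-width 0.145
- n = 60, 50 non-responders: 0.715 to 0.917, half-width 0.101

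**The case against.** The strongest reply is that the objective's wording describes one two-stage predictor. The primary objective is phrased similarly, with TUVglobal before therapy and at Week 5, and a single bucketing result meets it. On that reading the quantitative side of the model already contains baseline. This is a fair reading, and it narrows the point without removing it: the visual read still has no stated time point, baseline category or rule. The same documents also treat TUVglobal[b] as a predictor in its own right.

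A reader might go further than the documents allow in four ways.

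- *That there is one visual result per patient.* Listing 28 is by patient and reader and has a date/time column, so repeat rows are not excluded. But no table or model is specified to use a baseline row.
- *That baseline visual data are thrown away.* Listing 25 shows an image finding by visit and Listing 26 shows reader results by imaging time point and joint. Both are headed SPECT/CT although the protocol acquires planar images, and both are listings only. What is shown is a missing analysis, not lost data.
- *That the trial should test whether the visual read can replace the cut-off of 5.* The objective asks about additive effect only.
- *That all 60-120 discordant patients can be pooled for a tighter estimate (about ±10 to ±7 points).* Pooling mixes visual-negative/TUV-positive with visual-positive/TUV-negative patients, so a single rate cannot show which read is right.

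It is also true that the documents define no visual criterion for baseline non-response, so one would have to be written. The objective has no matching entry in the secondary endpoint lists and no alpha, which limits its weight.

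**Conclusion.** The point holds. The baseline half of this secondary objective has no variable, table or model term, and this is so on either reading of the objective. It is more than missing detail, because the plan followed exactly cannot answer that half, and a baseline-only call may not be recoverable later.

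The consequence is limited to this objective. The co-primary sensitivity and specificity and the key secondary NPV use TUV alone and do not change. It should be corrected, but it does not threaten the trial's main conclusions.

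The conclusion rests on the SAP text and shells and needs no numerical assumption. The illustration of roughly ±14.5 to ±10 points per discordant direction depends on the assumed 10-20% disagreement, an even split, 600 completers and the 5:1 ratio. It indicates only that the comparison would be informative but not precise.

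**What to change.** - **Record the read.** Before the Week 5 image is opened, each reader records a baseline visual prediction of non-response (yes/no) under a written criterion. Add a visit field to Listing 28.
- **Tabulate it.** By reader, cross-tabulate that prediction with TUVglobal[b] < 5 against Week 24 ACR50, showing the two discordant directions separately.
- **Model it.** By reader, fit a logistic model: logit P(ACR50 at Week 24) = b0 + b1·(TUVglobal[b] < 5) + b2·(baseline visual non-response). Test b1 given b2 and b2 given b1. Continuous TUVglobal[b] may be added as a supplement; the pre-specified cut-off stays as the main term.

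The cost is a short reader instruction, one extra recorded item and a few tables, with no additional scan, reader or patient.

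If Week 5 images have already been read without a baseline-only call, limit the stated objective in Protocol 2.3 and SAP 1.0 to the Week 5 change instead. That costs only the wording, but gives up the baseline question.
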